3.3.4.2 Cohort 2 (Single-Agent Expansion)

Cohort 2 will begin enrollment after the RD of lenvatinib is identified in Cohort 1. The efficacy of lenvatinib will be evaluated in 2 malignancy groups separately: DTC (Cohort 2A)

and osteosarcoma (Cohort 2B). Subjects will be treated at the RD identified in Cohort 1. The RD of Single-Agent lenvatinib determined in Cohort 1 is 14 mg/m^2 as recommended by TiTE-CRM and confirmed by PSC. Subjects in Cohorts 2A and 2B will receive 14 mg/m^2 lenvatinib (equivalent to 24 mg QD, adult daily dose). After adjustment for BSA, the daily dose should not exceed 24 mg QD.

3.3.4.3 Cohort 3A: Combination Dose-Finding

Lenvatinib will be administered orally QD in combination with ifosfamide and etoposide from Day 1 to Day 3 of each cycle for a total of 5 cycles to subjects with relapsed or refractory osteosarcoma as described below and in Table 2 See Protocol Section 9.4.3 for additional details on cytotoxic chemotherapy.

Table 2 Lenvatinib and Chemotherapy Doses for Combination Dose-Finding (Cohort 3A)

Dose Modification of Lenvatinib				
	Dose - Escalation	Starting Dose	De-escalation 1	De-escalation 2
Lenvatinib	RD (from Cohort 1)	20% lower than RD from Cohort 1	40% lower than RD from Cohort 1	60% lower than RD from Cohort 1

Dose Modification of Ifosfamide and Etoposide				
	No Dose Escalation	Starting Dose	De-escalation 1*	De-escalation 2*
Ifosfamide		$3000 \text{ mg/m}^2/\text{day}$ IV for 3 days	$2400 \text{ mg/m}^2/\text{day}$ IV for 3 days	$1800 \text{ mg/m}^2/\text{day}$ IV for 3 days
Etoposide		$100 \text{ mg/m}^2/\text{day}$ IV for 3 days	$80 \text{ mg/m}^2/\text{day}$ IV for 3 days	$60 \text{ mg/m}^2/\text{day}$ IV for 3 days

RD = recommended dose, *each De-escalation dose level is 20% lower than the Starting Dose.

The chemotherapy cycles will be repeated every 21 days.

Lenvatinib is administered daily as a QD dose, and ifosfamide and etoposide will be administered on Days 1 to 3 of each cycle for a total of 5 cycles. Each Chemotherapy cycle is repeated every 21 days. Six subjects with osteosarcoma (who have not received prior lenvatinib) will be enrolled first to Cohort 3A at the Starting Dose of lenvatinib (20% below the Single-Agent RD in Cohort 1) in combination with ifosfamide $3000 \text{ mg/m}^2/\text{day}$ for 3 days (ifosfamide total dose 9 g/m^2) and etoposide $100 \text{ mg/m}^2/\text{day}$ for 3 days (etoposide total dose 300 mg/m^2). Subjects with lenvatinib dose capped after BSA adjustment (dose must not exceed 24 mg daily) actually take lower dose level than assigned. If a subject with capped dose experiences a DLT, the DLT data from that subject will be counted to determine the RD of the combination treatment. A subject with capped dose who does not experience a DLT will be replaced for the purpose of determining the RD.

DLTs occurring during Cycle 1 will be evaluated and the next 6 subjects will be assigned a dose based on the rules for Dose Escalation and Dose De-Escalation as follows:

- a. If ≤ 1 out of 6 subjects experiences a DLT at the starting dose during Cycle 1 (Day 1 to Day 21), then assign 6 more subjects to the next higher dose level of lenvatinib (RD from Cohort 1) and keep the chemotherapy dose the same (starting dose).
- b. If ≥ 2 out of 6 subjects experience a DLT at the starting dose during Cycle 1 (Day 1 to Day 21), then follow the instructions below;
 - i. If ≥ 2 subjects experience hematologic DLT and ≤ 1 subject experiences non-hematologic DLT, then assign 6 more subjects to 20% lower doses (De-escalation 1) of ifosfamide and etoposide and keep the lenvatinib dose the same; or
 - ii. If ≥ 2 subjects experience non-hematologic DLT and ≤ 1 subject experiences a hematologic DLT, then assign 6 more subjects to a 20% lower dose of lenvatinib (De-escalation 1) and keep the ifosfamide and etoposide doses the same; or
 - iii. If ≥ 2 subjects experience hematologic DLTs and ≥ 2 subjects experiences non-hematologic DLTs, then assign 6 more subjects to 20% lower doses of lenvatinib, ifosfamide, and etoposide each (De-escalation 1); or
 - iv. If only 1 subject experiences a hematologic DLT and only 1 subject experiences a non-hematologic DLT, then assign 6 more subjects to the same dose level of lenvatinib, ifosfamide and etoposide each.
- c. Continue the above processes until the combination dose of lenvatinib, ifosfamide and etoposide results in ≤ 1 DLT per 6 subjects or only 1 subject experiences a hematologic DLT and only 1 subject experiences a nonhematologic DLT per 6 subjects upon repeating the same dose level. This dose will be considered as the RD of the combination treatment.

Once the RD has been determined, subjects treated at a lower dose level should continue to be treated at that dose level. Intrasubject dose-escalation is not permitted. Further dose de-escalation of lenvatinib or the chemotherapy dose may be considered (pending discussion with the Protocol Steering Committee [PSC]), if needed.

3.3.4.4 Cohort 3B (Combination Expansion)

Subjects with either lenvatinib-naïve relapsed or refractory osteosarcoma or osteosarcoma subjects who progress on single-agent lenvatinib in Cohorts 1 or 2B (optional enrollment) will receive lenvatinib (at the RD identified from Cohort 3A) in combination with ifosfamide and etoposide, provided the combination of lenvatinib, ifosfamide, and etoposide in Cohort 3A (Combination Dose-Finding) is determined to be safe and tolerable.

Osteosarcoma subjects who experience progressive disease in Cohorts 1 or 2B and choose to receive the combination therapy of lenvatinib with ifosfamide and etoposide should meet only inclusion criteria numbers 6 through 17 and all the exclusion criteria except Criterion Number 6.

Subjects in Cohorts 3A and 3B will receive ifosfamide and etoposide for a maximum of 5 cycles. Subjects who discontinue ifosfamide and etoposide in Cohorts 3A and 3B (e.g., due to toxicity) prior to completing 5 cycles may continue on single-agent lenvatinib if they are benefiting from the treatment at the discretion of the investigator. Subjects who discontinue lenvatinib prior to completing 5 cycles may continue on ifosfamide and etoposide at the investigator's discretion for 5 cycles.

3.3.5 Post-treatment (All Cohorts)

The Post-treatment Follow-up begins when the subject discontinues treatment. After subject discontinues treatment, an Off-Treatment Visit and the procedures noted in the Schedule of Assessments Tables (see Protocol Table 7, Table 8, and Table 9) should be completed within 30 days after the last dose of drug. Subjects will be followed for survival every 3 months until death or for 1 year, whichever occurs first, unless the study is terminated or the subject discontinues due to withdrawal of consent or is lost to follow-up (see Protocol Section 9.3.3).

Subjects who discontinue treatment without disease progression will have tumor assessments performed every 6 or 8 weeks (per the appropriate tumor assessment schedule) for up to 1 year, or sooner if clinically indicated, for documented disease progression or until another anticancer therapy is initiated whichever occurs first. After data cutoff, tumor assessments may be performed as clinically indicated using the institutional guidelines, following the prevailing local standard of care.

As required by some regulatory agencies, the following estimates are provided:

- The study will begin in December 2014 and will end on or before December 2017 (revised estimate is April 202).
- The maximum estimated period for the study is anticipated to be approximately 36 months. However, subjects will continue to receive study treatment as long as they demonstrate clinical benefit. Subjects benefiting from study treatment in the opinion of the investigator will continue to receive treatment until disease progression, intolerable toxicity, subject noncompliance with safety or efficacy assessments, initiation of another anticancer therapy, voluntary discontinuation by the subject at any time, or study termination by the sponsor, whichever occurs first.

3.4 Doses for Cohorts 2A, 2B, 3A, and 3B

3.4.1 Doses for Cohorts 2A and 2B

The RD of single-agent lenvatinib determined in Cohort 1 is 14 mg/m² as recommended by the TiTE-CRM and confirmed by the PSC.

Cohorts 2A and 2B will receive 14 mg/m² lenvatinib (equivalent to 24 mg QD, the adult daily dose). After adjustment for BSA, the daily dose should not exceed 24 mg QD.

3.4.2 Doses for Cohorts 3A and 3B

The RD of the combination with ifosfamide and etoposide determined in Cohort 3A is lenvatinib 14 mg/m²/day + ifosfamide 3000 mg/m²/day and etoposide 100 mg/m²/day as recommended by the above rules and confirmed by the PSC.

Cohort 3B will receive lenvatinib 14 mg/m²/day + ifosfamide 3000 mg/m²/day and etoposide 100 mg/m²/day.

3.5 Toxicity Management

Toxicity will be managed by treatment interruption, dose reduction and/or treatment discontinuation. Dose reduction and interruption for subjects who experience lenvatinib-related toxicity and ifosfamide/etoposide-associated toxicity will be in accordance with the protocol-specified dose reduction and interruption instructions (Sections 9.4.1.2 and 9.4.1.11 of the Protocol).

4 DETERMINATION OF SAMPLE SIZE

Cohort 1: Approximately 12 to 24 subjects based on the TiTE-CRM algorithm in the single-agent dose-finding cohort.

Cohort 3A: Approximately 12 to 24 subjects with osteosarcoma will be enrolled in combination dose-finding cohort.

Cohort 2A: Approximately 12 subjects with evaluable or measurable disease are planned to be enrolled in the DTC cohort.

Cohort 2B: A minimum of 15 PFS-4 evaluable subjects will be assessed in the osteosarcoma single-agent expansion. The sample size estimates were based on Simon's Optimal Two-Stage Design ([Simon, 1989](#)). If < 5 subjects achieve PFS-4 among the 15 evaluable subjects in Stage I, accrual in the cohort will be suspended. Otherwise, if at any time during Stage I of the cohort, ≥ 5 subjects achieve PFS-4 among the 15 evaluable subjects, enrollment in the cohort will continue for a total of approximately 27 evaluable subjects. If, at the end of the second stage for the cohort, ≥ 10 subjects achieve PFS-4 among the 27 subjects in the cohort, lenvatinib will be considered active in the population. The above sample size estimates are based on the following assumptions: the null hypothesis PFS-4 (H_0) is $\leq 25\%$, and the alternative hypothesis PFS-4 (H_1) is $\geq 45\%$. One-sided Type I error (α) = 0.1, and power = 80%. To account for nonevaluable subjects, a total of 15-30 osteosarcoma subjects will be enrolled in Cohort 2B.

Cohort 3B: With the following assumptions: $p_0 = 25\%$, $p_1 = 50\%$, 1-sided $\alpha = 10\%$, $\beta = 20\%$, where p_0 is an unacceptable rate of PFS, p_1 is the target rate of PFS, α is the probability of declaring lenvatinib effective when the true rate is p_0 , and β is the probability of declaring

lenvatinib not effective if the true rate is p_1 , a sample size of 15 subjects will provide a statistical power of 80%. To account for nonevaluable subjects, a total of 18 lenvatinib-naïve subjects will be enrolled in the combination expansion, along with some subjects from Cohorts 1 and 2B.

5 STATISTICAL METHODS

All descriptive statistics for continuous variables will be reported using n, mean, SD, median, 25th percentile (Q1), 75th percentile (Q3), minimum and maximum. Categorical variables will be summarized as number (percentage) of subjects. The statistical analyses of the study data as described in this section will be performed as further outlined in this SAP, which will be finalized before database lock and be included in the CSR.

Efficacy will be evaluated based on the Full Analysis Set (see SAP [Sections 5.2.1](#) and [7.2](#)). Each cohort will have its own cutoff date for the final analysis for CSR reporting purposes. For Cohorts 1 and 3A, the data cutoff will occur when the RD is determined and the last enrolled subject completes 6 cycles of treatment or discontinues before the end of Cycle 6, whichever occurs first or pending discussion with the PSC. For DTC and osteosarcoma subjects in Cohorts 2A, 2B, and 3B, the cutoff will be after all subjects enrolled have either completed 6 cycles or have discontinued treatment before the end of Cycle 6, whichever occurs first.

5.1 Study Endpoints

5.1.1 Primary Endpoints

For Cohort 1, the primary endpoint is RD of lenvatinib based on the TiTE-CRM design. While for Cohort 3A, it is RD of the combination treatment (lenvatinib + etoposide + ifosfamide).

For the three Phase 2 cohorts, the primary endpoints are:

- Cohort 2A (DTC): ORR, ie, the proportion of subjects who have a BOR of complete response (CR) or partial response (PR) for subjects with measurable disease and BOR for all subjects based on RECIST 1.1
- Cohort 2B (Osteosarcoma): PFS-4, ie, the percentage of subjects evaluable for PFS-4 who are alive and without PD at 4 months from the first dose based on RECIST 1.1. Subjects evaluable for PFS-4 includes those treated at least 4 months or those who died or radiologically progressed within 4 months after first dose.
- Cohort 3B: PFS-4

5.1.2 Secondary Endpoints

- Efficacy endpoints:

- BOR over the treatment period (except for Cohort 2A): defined as the best response recorded from the start of study drug until 30 days after the last dose or until PD, whichever occurs earlier
- ORR (except for Cohort 2A): defined as the proportion of subjects who have BOR of CR or PR
- DOR: defined as the time from first documentation of tumor response (CR or PR) to PD
- Disease Control Rate (DCR): defined as the percentage of subjects with measurable disease who have a BOR of CR or PR or stable disease (SD) or subjects with evaluable disease who have a BOR of CR or Non-CR/Non-PD. To be assigned a BOR of SD or Non-CR/Non-PD, the time from the first administration of study drug until the date of documented SD or Non-CR/Non-PD should be ≥ 7 weeks
- Clinical Benefit Rate (CBR): defined as the percentage of subjects with measurable disease who have a BOR of CR or PR or durable SD lasting ≥ 23 weeks or subjects with evaluable disease who have a BOR of CR or durable Non-CR/Non-PD lasting ≥ 23 weeks
- TTP: defined as the time from the date of the first administration of study drug until the date of first documentation of PD.
- PFS: defined as the time from first dose to documented date of PD or death (whichever occurs first)
- Safety endpoints:
 - Adverse events (AEs), serious AEs (SAEs), clinical laboratory values, vital signs, 12-lead electrocardiograms (ECGs), urine dipstick, occult blood in stool, echocardiogram, Lansky play scores or Karnofsky performance status (KPS), physical examination findings, and height, and closure of proximal tibial growth plates during treatment and follow-up.
 - Plasma lenvatinib exposure parameters
 - Assessment of blood or tumor biomarkers that correlate with clinical response to lenvatinib treatment or AEs associated with lenvatinib treatment
 - Palatability and acceptability of the suspension formulation of lenvatinib

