- Assessment of blood or tumor biomarkers that correlate with clinical response to lenvatinib treatment or AEs associated with lenvatinib treatment

Cohorts 2A and 2B

- Efficacy
 - BOR over the treatment period (osteosarcoma group)
 - ORR (measurable osteosarcoma group)
 - DOR (measurable DTC and osteosarcoma group)
 - Disease Control Rate (DCR) defined as the percentage of subjects with measurable disease who have a BOR of CR or PR or stable disease (SD) or subjects with evaluable disease who have a BOR of CR or Non-CR/Non-PD. To be assigned a best overall response of SD or Non-CR/Non-PD, the time

from the first administration of study drug until the date of documented SD or Non-CR/Non-PD should be ≥ 7 weeks.

- Clinical Benefit Rate (CBR) defined as the percentage of subjects with measurable disease who have a BOR of CR or PR or durable SD lasting ≥ 23 weeks or subjects with evaluable disease who have a BOR of CR or durable Non-CR/Non-PD lasting ≥ 23 weeks
- PFS defined as the time from the date of the first administration of study drug to the date of first documentation of disease progression or date of death, whichever occurs first
- TTP defined as the time from the date of the first administration of study drug until the date of first documentation of disease progression
- OS defined as the time from the date of the first administration of study drug until the date of death from any cause. Subjects who are lost to follow-up and those who are alive at the date of data cutoff will be censored at the date the subject was last known to be alive (or the data cutoff date).
- Safety
 - AEs, SAEs, clinical laboratory values, vital signs, 12-lead ECGs, urine dipstick, occult blood in stool, Lansky play scores or Karnofsky performance scores, physical examination findings, and height and closure of proximal tibial plates during treatment and follow-up
 - Plasma lenvatinib exposure parameters
 - Assessment of blood or tumor biomarkers that correlate with clinical response to lenvatinib treatment or AEs associated with lenvatinib treatment

Cohorts 3A and 3B

- Efficacy
 - BOR over the treatment period
 - ORR (osteosarcoma group)
 - DOR

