5.2 Study Subjects

5.2.1 Definitions of Analysis Sets

The following analysis sets will be defined:

- **Full Analysis Set** includes all enrolled subjects who have not failed study screening. Demographic and baseline characteristics, previous anticancer medications, prior and concomitant medications, procedures and radiotherapy, medical history, and efficacy analyses will primarily be based on the Full Analysis Set.
- **Per Protocol Analysis Set** includes those subjects who (1) receive at least 1 dose of the assigned study drug; (2) have no major protocol deviations; (3) had both Baseline and at least 1 postbaseline tumor assessment. This will be the secondary analysis set for all tumor response-related efficacy endpoints.
- **Safety Analysis Set** includes all subjects who received study drug. This will be the analysis set for all safety evaluations.
- **Palatability Analysis Set** includes all subjects who received oral suspension of lenvatinib and answered at least 1 question in the Palatability Questionnaire CRF.
- **Pharmacokinetic (PK) Analysis Set** includes all subjects who have received at least 1 dose of any study drug and have evaluable lenvatinib concentration data.

This additional analysis set will be defined for Cohort 1:

- **DLT Analysis Set** includes all subjects who either a) experience DLT during Run-in Period or Cycle 1 or b) receive all scheduled doses of study drug on their scheduled days during Cycle 1 and complete Cycle 1 observation period without a DLT.

This additional analysis set will be defined for Cohort 3A:

- **DLT Analysis Set** includes all subjects who either a) experience DLT during Cycle 1 or b) receive all scheduled doses of study drug on their scheduled days during Cycle 1 and complete Cycle 1 observation period without a DLT.

See [Section 7.2](#) explaining the analysis sets in addition to those listed in the protocol.

The number and percentage of subjects included in each analysis set will be presented by cohort and dose level in Phase 1 and by cohort in Phase 2. A listing will also be provided to identify subjects in each analysis set.

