5.4.2 Efficacy Analyses

The tumor response data used in the primary analyses of the PFS-4 rate and ORR will be obtained from the investigator's assessment of the imaging scans. No independent tumor assessments will be performed as part of this study. Tumor response will be assessed by RECIST 1.1. All the efficacy analyses will be performed on the Full Analysis Set, and the Per Protocol Analysis Set for all tumor response-related efficacy endpoints. A tabular summary of key features of the efficacy analyses is described in SAP [Appendix 13.2 \(Summary of Efficacy Analyses\)](#).

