5.4.2.2 Secondary Efficacy Analyses

The secondary efficacy endpoints include BOR over the treatment period (except for Cohort 2A), ORR (except for Cohort 2A), DCR, and CBR, as well as DOR (measurable disease only). PFS and TTP are defined in SAP [Section 5.1](#) and will be performed for subjects in the Full Analysis and Per Protocol Analysis Sets.

Subjects who do not have a tumor response assessment for any reason will be considered nonresponders and will be included in the denominator when calculating the response rate. The count and percentage for ORR will be summarized by dose level for Cohorts 1 and 3A and by cohort for Cohorts 2B and 3B. ORR and corresponding 95% CI based on the exact binomial distribution will be estimated for all corresponding treatment cohorts.

The count and percentage for both the DCR and CBR will be summarized for each treatment cohort, along with the exact 95% CI for.

The median and quartiles of DOR will be estimated by the Kaplan-Meier (KM) method ([Kaplan and Meier, 1958](#)), and the 95% CI estimated with a generalized Brookmeyer and Crowley method ([Brookmeyer and Crowley, 1982](#)).

For PFS, if a subject has not experienced PD or death, then the subject's data will be censored on the date of the last adequate radiologic assessment.

TTP will be calculated using data from all subjects in the Full Analysis Set. The calculation for TTP does not classify deaths as events.

The PFS censoring rules in this SAP and definition of progression date follow the [Food and Drug Administration \(FDA\), Guidance for Industry Clinical Trial Endpoints for the Approval of Cancer Drugs and Biologics \(2007\)](#) (See SAP Table 3). The PFS censoring rules are referenced in SAP Table 3 and TTP censoring rules are referenced in SAP Table 4.

Table 3 Censoring Rules for Analysis of Progression-Free Survival

No	Situation	Date of Progression or Censoring	Outcome
1	No baseline tumor assessments	Date of first dose	Censored
2	No postbaseline tumor assessments	Date of first dose	Censored
3	Progression documented between scheduled visits	Date of first radiologic PD assessment	Progressed
4	More than 1 NE tumor timepoint assessment	Date of last adequate radiologic assessment before NE tumor assessments	Censored
5	No progression at time of data cutoff	Date of last adequate radiologic assessment	Censored
6	New anticancer treatment started	Date of last adequate radiologic assessment prior to or on date of new anticancer treatment	Censored

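### For Cohort 2B the SAP drops the protocol's restriction of secondary ORR to measurable osteosarcoma, so subjects who cannot have a PR enter the denominator; for Cohorts 3A/3B the protocol disagrees with itself on the same restriction

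*SAP*

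**What the plan says.** **Protocol.** For Cohort 2, the secondary endpoint in Section 9.7.1.1 is "ORR (measurable osteosarcoma group", and the synopsis uses the same wording. For Cohorts 3A/3B the synopsis again restricts ORR to measurable disease, but Section 9.7.1.1 names only the osteosarcoma group. For Cohort 1 both places list ORR with no qualifier. Inclusion criterion 3 admits subjects with either evaluable or measurable disease.

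**SAP.** In Section 5.1.2, ORR for every cohort except 2A is "defined as the proportion of subjects who have BOR of CR or PR". Section 5.4.2 states "All the efficacy analyses will be performed on the Full Analysis Set", with the Per Protocol set used as well for response endpoints. Section 5.2.1 says the Full Analysis Set "includes all enrolled subjects who have not failed study screening". Section 5.4.2.2 adds that subjects without a response assessment "will be considered nonresponders and will be included in the denominator when calculating the response rate". The ORR row of Appendix 13.2 has no measurable-disease condition.

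The SAP does apply the condition elsewhere: to the primary ORR of Cohort 2A (Section 5.1.1) and to duration of response, "DOR (measurable disease only" (Section 5.4.2.2). Section 7, which lists departures from the protocol, covers PFS-4 in Cohort 3A, the added analysis sets, and the growth-plate and palatability listings. It does not mention the ORR population.

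**The concern.** The DCR and CBR definitions in both documents give evaluable-only subjects two favourable outcomes, CR or Non-CR/Non-PD. PR is not open to them. Counting them in an ORR denominator adds subjects for whom one of the two qualifying outcomes is impossible, which is a natural reason for the protocol's restriction.

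At stake is the meaning of the reported figure. The Cohort 2B ORR would carry the protocol endpoint's name but describe a different population, and it would be expected to come out lower. In a cohort of 15 to 30 subjects a few non-measurable cases move the percentage visibly. Readers are likely to set it beside the osteosarcoma response rates cited in protocol Section 7.1.3, which run from 9% to 48%.

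**Working it through.** The documents give no target, sample size or power for ORR, so there is no figure of the plan's own to reproduce. The check has two parts: a comparison of the texts, and an illustration of size.

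**1. Texts side by side**

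| Cohort | Protocol synopsis | Protocol 9.7.1.1 | SAP 5.1.2 and 13.2 |
|---|---|---|---|
| 1 | no limit | no limit | no limit |
| 2B | measurable | measurable | no limit |
| 3A/3B | measurable | no limit | no limit |

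Only for Cohort 2B does the SAP depart from a protocol that is consistent across its two endpoint lists. For 3A/3B it matches the body and departs from the synopsis. For Cohort 1 there is no departure.

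**2. Direction of the effect**

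Let m be the share with measurable disease, R the ORR among them, and C the CR rate among evaluable-only subjects. Then

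ORR over all subjects = m × R + (1 − m) × C

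This is below R exactly when C < R. If C = 0 it equals m × R, a relative reduction of 1 − m.

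**3. Size in Cohort 2B**

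Inputs: N = 30, the top of the planned range (SAP Section 4); 3 responders, all with measurable disease, chosen for illustration; C = 0; non-measurable share 10% to 40%, an assumption because the documents give none. Intervals are Clopper-Pearson 95%. Over all subjects the result is 3/30 = 10.0% (2.1 to 26.5).

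| Non-measurable | Measurable-disease ORR | 95% CI |
|---|---|---|
| 3 (10%) | 3/27 = 11.1% | 2.4 to 29.2 |
| 6 (20%) | 3/24 = 12.5% | 2.7 to 32.4 |
| 9 (30%) | 3/21 = 14.3% | 3.0 to 36.3 |
| 12 (40%) | 3/18 = 16.7% | 3.6 to 41.4 |

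Check against the formula at 20%: 0.80 × 12.5% = 10.0%.

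**4. The effect is not automatic**

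Take the 20% row and suppose one of the 6 evaluable-only subjects has a CR. Then C = 1/6 = 16.7%, which exceeds R = 12.5%, and the all-subject rate is 4/30 = 13.3%. In that case the SAP's figure is the higher one.

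**5. Cohort 3B, if the synopsis is what was meant**

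With N = 18 and 3 responders the all-subject rate is 3/18 = 16.7%. The measurable-disease rate is 3/14 = 21.4% with 4 non-measurable, and 3/11 = 27.3% with 7.

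**The case against.** The best defence is that the SAP is silent rather than contrary. Section 5.1.2 says subjects, not all subjects. Its entry for duration of response also omits a limit that Section 5.4.2.2 then supplies, and the single ORR row of Appendix 13.2 is not split by cohort although the Cohort 2A ORR is restricted. Omission there is weak evidence of intent. This stands as to intent. It does not settle the calculation: a programmer following the definition, the Full Analysis Set and the appendix would use every enrolled subject. Nor can the parenthesis in "as well as DOR (measurable disease only" be stretched to ORR, because the same list contains DCR and CBR, which include evaluable disease by definition.

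The protocol is also mixed beyond its endpoint lists. The Cohort 2 secondary objectives (Section 8.2) and Section 9.2 attach the measurable condition to duration of response and not to ORR, and the analysis text in Section 9.7.1.5 sets no such denominator. That is a reason to tidy the protocol. For 2B, however, the endpoint definitions themselves agree.

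The SAP says it is based on Amendment 03, and the version of the protocol supplied is not visible. The difference could reflect versions, but the documents should still agree or the change be declared.

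A reader might infer several stronger points that the documents do not support:

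- That Cohort 1 loses a restriction as well. Its protocol ORR never had one.
- That the SAP contradicts the whole protocol for 3A/3B. It conflicts with the synopsis only.
- That keeping unassessed subjects in the denominator is part of the fault. That rule is conservative and works equally well within measurable disease.
- That dilution is certain. Evaluable-only subjects can still contribute a CR.
- That comparison with Cohort 2A suffers. Thyroid cancer and osteosarcoma are evaluated separately and no comparison is planned.

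**Conclusion.** The point holds for Cohort 2B: the SAP as written replaces the protocol's measurable-disease ORR with a rate over the Full Analysis Set and does not declare it. For Cohorts 3A/3B the finding is an inconsistency within the protocol that has to be resolved before the SAP can be called right or wrong.

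The expected effect is a lower ORR. Its size rests on two assumptions: the non-measurable share, which the documents do not give, and no CRs in evaluable-only disease. Under both, an assumed share of 10% to 40% lowers ORR by 10% to 40% in relative terms. Any CR among evaluable-only subjects reduces this and can reverse it.

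The consequence is limited to reporting. ORR in this cohort is descriptive, with no hypothesis test, decision rule or sample size attached, and the primary endpoint, PFS-4, is untouched.

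**What to change.** In SAP Sections 5.1.2 and 5.4.2.2 and Appendix 13.2, define Cohort 2B ORR among Full Analysis Set subjects with measurable disease at baseline. Keep measurable subjects without a response assessment as nonresponders, and report the all-subject ORR as a supplement. Align protocol Section 9.7.1.1 with the synopsis for Cohorts 3A/3B, then apply the same definition there. If the all-subject denominator was intended, state and justify it in SAP Section 7 instead.

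The cost is SAP wording and a denominator filter. No new data are needed, since DCR, CBR and the Cohort 2A ORR already require each subject to be classed as measurable or evaluable-only. The statistical price is wider confidence intervals, noticeably so if the non-measurable share is large: with 3 responders, 2.1 to 26.5% on 30 subjects against 3.6 to 41.4% on 18.
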